4 STUDY DESIGN

This 30-day, Phase IIa, two-arm, randomized, placebo-controlled, single-blinded, superiority treatment study in 136 males and non-pregnant females ≥ 18 to 65 years of age will compare placebo to once daily doses of auranofin (Ridaura) for adults with amebiasis (68 subjects) or giardiasis (68 subjects). Potential Bangladeshi adult subjects will be identified by a health professional from otherwise stable patients presenting to the icddr,b or Rajshahi Medical College Hospitals with diarrhea (thought to be due to amebiasis or giardiasis). Rajshahi Medical College Hospital is being added as a new enrollment site because of their higher prevalence of amebic infections (Alam et al., 2014). Eligible subjects will be randomly assigned to a treatment group with auranofin (6 mg orally once daily for 5 days for giardiasis or 7 days for amebiasis) compared to a placebo group receiving similar but not identical placebo capsules. Projected duration of subject participation will be approximately 30 days of face to face visits, including the pre-enrollment screening period of up to 4 days. It is anticipated that it will take approximately 3.5 years to finish the study.

Primary and secondary outcomes to be measured during the course of the study are outlined in Section 3.2.

For additional details on study procedures and evaluations by study schedule and study visits see Section 7, 8, and Appendix A.

4.1 Sub Studies

No sub studies are planned.

5 STUDY ENROLLMENT AND WITHDRAWAL

One hundred thirty six males and non-pregnant females, aged 18-65 years, with amebiasis or giardiasis who are otherwise healthy and meet all eligibility criteria, will be chosen from adult patients presenting to the iccdr,b or Rajshahi Medical College Hospitals with mild diarrhea.

Subject Inclusion and Exclusion Criteria must be assessed by a study clinician licensed to make medical diagnoses and listed on the Form FDA 1572 as the site principal investigator or sub-investigator.

No exemptions are granted on Subject Inclusion/Exclusion Criteria in DMID-sponsored studies. Questions about eligibility should be directed toward the DMID Medical Officer.

5.1 Subject Inclusion Criteria

Subjects eligible to participate in this study must meet all of the following inclusion criteria:

1. Provide written informed consent prior to initiation of any study procedures.
2. Able to understand and comply with planned study procedures and be available for all study visits.
3. Male or non-pregnant, non-lactating females 18-65 years of age, inclusive. Females of reproductive potential currently using effective contraceptive methods are eligible.
4. Amebiasis or giardiasis identified by rapid EIA and positive antigen detection EIA of stool^{1,1}

¹If a subject is infected with both *E. histolytica* and *Giardia*, they will be enrolled in the *E. histolytica* study arm. Once the *Entamoeba* study arm is fully enrolled, any subsequent dual infected subjects will be enrolled in the *Giardia* arm. If a subject is infected with both *Giardia* and *Cryptosporidium*, they will not be enrolled.

5. Has diarrhea (defined as three or more loose stools) in the past 24 hrs, but is assessed to be clinically stable and in otherwise good health².

²As determined by medical history and targeted physical examination, if indicated based on medical history, to evaluate acute or currently ongoing chronic medical diagnoses or conditions that would affect the assessment of eligibility and safety of subjects. Existing

medical diagnoses or conditions (except those in the Subject Exclusion Criteria) must be deemed as stable chronic medical conditions. A stable chronic medical condition is defined as no change in prescription medication, dose, or frequency of medication in the last 3 months (90 days) and health outcomes of the specific disease are considered to be within acceptable limits in the last 6 months (180 days). Any change due to change of health care provider, insurance company, or that is done for financial reasons, as long as in the same class of medication, will not be considered a violation of this inclusion criterion. Any change in prescription medication due to **improvement** of a disease outcome, as determined by the site principal investigator or appropriate sub-investigator, will not be considered a violation of this inclusion criterion. Subjects may be on chronic or as needed (prn) medications if, in the opinion of the site principal investigator or appropriate sub-investigator, they pose no additional risk to subject safety. *Topical, nasal, and inhaled medications, vitamins, and contraceptives are permitted.*

6. Vital signs (oral temperature, pulse, and blood pressure) are all within normal protocol-defined ranges (abnormal criteria defined in Section 9.2.3 Additional Adverse Event Severity Grading).
7. Laboratory tests (blood urea nitrogen, creatinine, AST, ALT, white blood cells, platelets, hemoglobin) are all within protocol-defined ranges.

Subjects will be eligible for enrollment with the following laboratory values:

- Blood urea nitrogen less than or equal to 30 mg/dL
 - Creatinine less than or equal to 133umol/L
 - AST or ALT less than or equal to 70.0 U/L
 - White cell count between 3.5 and 13.0 inclusive($10^9/L$)
 - Platelets between 131 and 550 ($10^9/L$) inclusive
 - Hemoglobin between 11.0 and 18.0 gm/dL inclusive
8. Urinalysis with no greater than trace protein. If a high protein is confirmed to be due to menstruation, it should be repeated.
 9. Women of reproductive potential⁴ must have a negative urine pregnancy test within 72 hours of starting study medications.

⁴Female subjects who are surgically sterile via tubal sterilization, bilateral oophorectomy or hysterectomy, who have been postmenopausal for greater than 1 year are not considered to be of reproductive potential.

10. Female subjects participating in sexual activity that could lead to pregnancy must be using and continue to use highly effective⁵ contraception for a total of 4 months after enrollment.

⁵Highly effective methods of contraception are defined as having low failure rates (i.e. less than 1% per year) when used consistently and correctly and may include, but are not limited to, abstinence from intercourse, monogamous relationship with a vasectomized partner, male condoms with spermicide, diaphragm with spermicide, intrauterine devices, and licensed hormonal methods. Females on effective forms of birth control will continue while on the study and for the follow-up period of 4 months total. The method and compliance of birth control used will be confirmed and documented at all study visits.

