7.1 Screening Visits

7.1.1 Visit 00A, Day -4 to -1, Screening 1, icddr,b or Rajshahi Medical College Hospitals

Potential adult subjects from Bangladesh (between the ages of 18-65) will be chosen from adult patients presenting to the icddr,b or Rajshahi Medical College Hospitals with mild diarrhea. These potential subjects will be visited by a study team member or health professional from icddr,b or Rajshahi Medical College Hospitals. Screening may take place as many as 4 days prior to enrollment. A 5-minute screener will be administered at the first screening visit and will be used to identify eligible persons who will be referred to a study team member to discuss inclusion in the study. Written informed consent will be obtained from potentially eligible subjects after the 5-minute screener and prior to conducting any further screening or study procedures. A single ICF will be used to document the volunteer's consent to further screening and participation in the study.

For subjects who are potentially eligible and who have provided informed consent, the following procedures will be conducted at the first screening visit:

- Full eligibility criteria will be reviewed with subjects.
- Demographic data, including date of birth, sex, self-reported ethnicity, and residence location will be collected.
- A stool sample will be collected for detection of *Giardia* or *E. histolytica*.

7.1.2 Visit 00B, Day -4 to -1, Screening 2, icddr, b or Rajshahi Medical College Hospitals

Only eligible subjects who have provided informed consent and stool specimens that are positive for *Giardia* or *E. histolytica* will have this second screening visit for blood and urine testing. This visit may also occur on the same day at Visit 00A and must occur at the hospital or clinic.

- Medical history will be obtained by interview of subjects to assure eligibility.
- All concomitant medications taken within 30 days prior to signing the informed consent form will be recorded on the appropriate data collection form and eCRF. Subjects will be questioned specifically about any metronidazole in the past 7 days.
- A targeted physical examination will be performed, including vital signs (oral temperature, pulse (taken at the wrist or neck), blood pressure) observation for rashes or glossitis, and an abdominal exam.
- A urine pregnancy test will be performed on all female subjects of childbearing potential and must be negative.

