- Approximately 17 mL of venous blood will be collected for CBC, ALT, AST, BUN, and creatinine tests. These values must be confirmed to meet the eligibility criteria as outlined in the Subject Inclusion Criteria (see Section 5.1) prior to randomization.
- A urine sample will be collected to test for the presence of protein. The result must be confirmed to meet the eligibility criteria as outlined in the Subject Inclusion Criteria (see Section 5.1) prior to randomization.

7.2 Visit 01, Day 1, Enrollment, Dose 1, icddr,b or Rajshahi Medical College Hospital or Clinic

- Enrollment and randomization of subjects
- Eligibility criteria, including results of all clinical screening laboratory evaluations, will be reviewed with subjects to assure continued eligibility.
- Targeted physical exam performed, if indicated
- 2 capsules of study product (6mg total) or placebo will be orally taken by the subject.
- Assessment of any new symptoms since Visit 00B before first dose is given.
- Medical history, including any concomitant medications, reviewed.
- Stool sample will be collected for ova and parasite testing. The window for stool specimens will be +1 day and the date of collection noted.

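### The only scheduled pregnancy test may be done on Day -4, too early to meet the 72-hour limit in inclusion criterion 9, and Day 1 has no repeat test

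*Protocol*

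**What the plan says.** Criterion 9 in Protocol 5.1 requires that women of reproductive potential "must have a negative urine pregnancy test within 72 hours of starting study medications". SAP 4.3.2.1 carries the same criterion. Section 5 allows no exemptions from the eligibility criteria, and Section 5.3.1 places randomization after eligibility has been confirmed.

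The test belongs to the second screening visit, headed "7.1.2 Visit 00B, Day -4 to -1, Screening 2". The instruction there is "A urine pregnancy test will be performed on all female subjects of childbearing potential and must be negative", with no limit on the age of the result. On timing, Section 7.1.1 says "Screening may take place as many as 4 days prior to enrollment", and Section 7.1.2 adds of Visit 00B that "This visit may also occur on the same day at Visit 00A and must occur at the hospital or clinic".

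The other places that mention the test agree:

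- Section 8.2.1 puts it at screening.
- Appendix A has a single mark for it, under Visit 00B, in the block whose window is Day -4 to -1.
- Appendix B lists it in the Visit 00B row, with the same window; its Day 1 row has stool tests only.
- SAP 9.5 describes a pregnancy test during screening and no other.

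At Visit 01 (Section 7.2) the site carries out a general check: "Eligibility criteria, including results of all clinical screening laboratory evaluations, will be reviewed with subjects to assure continued eligibility". It also makes an "Assessment of any new symptoms since Visit 00B before first dose is given" and reviews history and concomitant medications. No pregnancy test is listed.

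**The concern.** Two rules for the same test do not fit together. One caps its age at 72 hours when dosing starts. The other allows it up to four days before enrollment. A site can follow the visit schedule exactly and reach Day 1 with a result that is already too old, and nothing in the schedule then produces a fresh one.

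What is at stake is an eligibility deviation on a safety criterion. Section 2.3.1 classes auranofin as Category C, advises against its use in pregnancy, and names pregnancy testing as one of the measures against that risk. The Visit 00B test is the only one scheduled in the whole trial, so a result that is too old is not backed up by a later scheduled test.

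**Working it through.** There is no figure in the plan to reproduce; the check is calendar arithmetic on two stated limits.

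**Inputs**

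- Maximum age of the test at first dose: 72 h (Protocol 5.1, criterion 9).
- Permitted days for the test: Day -4 to Day -1 (Protocol 7.1.2; Appendix A, first block; Appendix B).
- First dose: Day 1, Visit 01 (Protocol 7.2).
- Day numbering: Section 7.1.1 puts screening at most four days before enrollment, so Day -4 is taken as four days before Day 1, with no Day 0.

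**Formula.** Let k be the number of calendar days from test to dose. At the same clock time the test is 24k hours old. With test and dose at any time on their respective days, its age lies strictly between 24(k - 1) and 24(k + 1) hours. The largest possible excess over the limit is 24(k + 1) - 72, or zero if that is negative.

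| Test day | k | Nominal age (h) | Range of age (h) | Against 72 h | Excess, at most (h) |
|---|---|---|---|---|---|
| Day -4 | 4 | 96 | 72 to 120 | always over | 48 |
| Day -3 | 3 | 72 | 48 to 96 | depends on clock time | 24 |
| Day -2 | 2 | 48 | 24 to 72 | never over | 0 |
| Day -1 | 1 | 24 | 0 to 48 | never over | 0 |

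The range ends are not attained, so every Day -4 test is strictly more than 72 h old.

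**Working hours.** The extremes above need a test or a dose near midnight. Assume instead that both fall between 08:00 and 17:00. The range is then nominal plus or minus 9 h:

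- Day -4: 96 ± 9 = 87 to 105 h, which is 15 to 33 h over.
- Day -3: 72 ± 9 = 63 to 81 h, at most 9 h over.
- Day -2: 48 ± 9 = 39 to 57 h, within the limit.
- Day -1: 24 ± 9 = 15 to 33 h, within the limit.

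**If a Day 0 were counted,** each k rises by one. Day -4 gives 96 to 144 h and Day -3 gives 72 to 120 h, both always over; Day -2 gives 48 to 96 h and can be over; Day -1 gives 24 to 72 h and is not. The Day -4 result fails under either numbering.

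**The second Appendix A header.** The continuation block gives Visit 00B as -3 to -1. The pregnancy-test row sits in the first block, under -4 to -1. With -4 to -1, one of four permitted days always fails and one of four can fail. With -3 to -1, none of three always fails and one of three can. Adopting the narrower window would therefore reduce the problem without removing it.

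These are counts of permitted days, not of women. The documents give neither the number of women of reproductive potential nor the distribution of screening days, so the number affected cannot be estimated.

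**The case against.** The strongest reply is that a strict rule inside a wider visit window is not a contradiction. Section 7.1.2 says when the visit may take place; criterion 9 says how recent the result must be. Both can be met by testing on Day -2 or Day -1, and often on Day -3. Criterion 9 binds, a study clinician must assess it, and the Day 1 review should expose a test that is too old. Section 5.3.1 bars screening a subject more than twice after a screening failure, which arguably leaves one rescreen open to a woman whose test has aged out.

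Most of this stands: the protocol does not authorise dosing on an older test. But reviewing results already in hand can show that a test is too old; it cannot replace it. The site must then turn away an otherwise eligible woman, rescreen her, retest her off schedule, or dose her with a deviation. Section 7.2 does not say which.

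The opposing case is also right about exposure. Visit 00B is for "Only eligible subjects who have provided informed consent and stool specimens that are positive for" one of the two parasites, so a Day -4 test needs consent, a positive stool and Visit 00B all on that day. A four-day wait follows, after which criterion 5 still requires diarrhea within the past 24 hours. Exclusion criterion 2 and inclusion criterion 10 require effective contraception, and Section 9.3.3 stops dosing if pregnancy is found. These points limit the severity; they do not close the gap.

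**Conclusion.** The concern holds, as a minor point. The schedule permits a test day, Day -4, that can never meet criterion 9 (nominally 96 h against 72 h), and another, Day -3, that may not meet it (48 to 96 h). Visit 01 has no scheduled test to correct either. The Day -4 conclusion needs no assumption about clock times and does not depend on whether a Day 0 is counted; the Day -3 range assumes no Day 0.

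The likely consequence is an occasional eligibility deviation or an avoidable screen failure. The safety risk is small, because contraception is required and few women are likely to follow the failing path, though the documents do not allow that number to be estimated. Randomization, power and the efficacy analysis are unaffected.

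**What to change.** In Section 7.2 add: *Repeat the urine pregnancy test before randomization and first dose if the Visit 00B test will be more than 72 hours old at dosing.* Add a matching conditional mark in the Day 1 column of Appendix A. This deals with Day -4 and Day -3 together, and criterion 9 stays as written.

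Give one Visit 00B window in both blocks of Appendix A, consistent with Section 7.1.2 and Appendix B.

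The cost is one line of text, one conditional mark, one corrected header and a few urine test strips. The SAP analysis does not change.

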5.2 Subject Exclusion Criteria

Subjects meeting any of the following exclusion criteria at baseline will be excluded from study participation within 1 week of the initial visit:

1. Known intolerance of auranofin or gold compounds.
2. Pregnant or breastfeeding women or women of reproductive potential not using effective contraception or who plan to become pregnant or breastfeed at any given time during the study or within 3 months of study completion.
3. Use of metronidazole within the past 7 days.
4. Has any condition that would, in the opinion of the site investigator, place the subject at an unacceptable risk of injury or render the subject unable to meet the requirements of the protocol.
5. Concurrent participation in other investigational protocols or receipt of an investigational product within the previous 30 days.
6. History of alcohol or drug abuse within the last five years.

5.3 Treatment Assignment Procedures

5.3.1 Enrollment and Randomization Procedures

Per International Conference on Harmonisation (ICH) guideline E6: Good Clinical Practice (GCP), screening records will be kept at the icddr,b or Rajshahi Medical College hospital site to document the reason why an individual was screened, but failed trial entry criteria. The reasons why individuals failed screening will be recorded in the Statistical and Data Coordinating Center's (SDCC) Advantage EDCSM (Electronic Data Capture System). No subject may be screened more than twice due to a screening failure result.

Randomization will be stratified by site to prevent confounding that could arise from imbalance in treatment allocations between sites. Because the relative pace of enrollment between the two sites is unknown, the number of participants to be enrolled at each site is not fixed in advance. With this approach, the faster enrolling site may enroll more subjects, allowing enrollment to complete as quickly as possible. Each site may enroll up to 68 subjects into each strata, so it is possible that one strata could be filled entirely with subjects from a single site. With the flexible approach, treatment assignments may not be perfectly balanced (overall or within each site), but they will be approximately balanced. With sample sizes of 68 in each strata, the impact of a small imbalance on power is negligible.

Once eligibility and consent are confirmed, subjects will be stratified by site and infection (a 2-level variable of either amebiasis vs. giardiasis), and then within each stratum, randomized 1:1 to receive auranofin or placebo on Day 1. Both disease groups will enroll concurrently. Enrollment will continue in the other arm after one arm reaches full enrollment. All subjects will receive doses of the assigned medication or placebo delivered orally on Days 1, 2, 3, 4, 5, 6, and 7 for amebiasis and Days 1, 2, 3, 4, and 5 for giardiasis.

The randomization code will be prepared by statisticians at the SDCC and included in the enrollment module for the trial. SDCC staff will generate two randomization lists and send corresponding documentation to the study site. The randomization lists will include the randomization codes that will be used to serially assign study treatment to subjects as they are assigned to the study (i.e., randomize subjects to study arm by study identification number). This table will not contain unblinded information; study staff will not be able to see the study arm assignment for each study identification number.

Eligible study subjects will be randomized under single-blind conditions by study staff members after consent. Since the placebo is similar but not identical to the study medication, only the lab

personnel are truly blind, however the participant will not be informed whether they receive study product or placebo. The randomization number will be recorded on the study CRFs.

A designated individual at icddr,b and Rajshahi Medical College hospital will be provided with the treatment key, which links the treatment code to the actual treatment assignment, which will be kept in a secure place.

5.3.2 Masking Procedures

This is a single-blind study because the placebo is similar, but not identical to the study drug. The laboratory personnel performing evaluations will be blinded to treatment assignment.

Subjects, investigators, and study personnel performing any study-related assessments following study product administration will not be informed of group allocation, but could detect differences in study and placebo capsules. They will be instructed to perform their clinical or AE assessments as though blinded to prevent potential bias.

The randomization scheme will be generated by the SDCC and provided to unblinded study personnel (i.e., study pharmacist).

The Data and Safety Monitoring Board (DSMB) may receive data in aggregate and presented by treatment group. The DSMB may also be provided with expected and observed rates of the expected AEs in an unblinded fashion. The DSMB may be unblinded to individual study treatment assignments, as needed, to adequately assess safety issues. Refer to the MOP for unblinding procedures.

5.3.3 Reasons for Withdrawal

Subjects may voluntarily withdraw their consent for study participation at any time and for any reason, without penalty. Subjects who have received study product, regardless of the number of doses received, or who developed an AE or SAE will be encouraged to remain in the study to be followed for safety purposes.

A subject may withdraw or be withdrawn from this study for any of the following reasons:

- Medical disease or condition, or any new clinical findings for which continued participation, in the opinion of the site principal investigator or appropriate sub-investigator, would compromise the safety of the subject, or would interfere with the subject's successful completion of the study, or would interfere with the evaluation of responses.

- Subject no longer meets eligibility criteria.
- As deemed necessary by the site principal investigator or appropriate sub-investigator for noncompliance or other reasons.
- Subject withdrawal of consent.
- Subject lost to follow-up.
- Termination of the study.
- New information becomes available that makes further participation unsafe.

A subject will be discontinued from further receipt of auranofin or placebo if:

- The subject misses more than one dose of drug or placebo.
- Any clinical adverse event, laboratory abnormality, intercurrent illness, other medical condition or situation occurs such that continued participation in the study would not be in the best interest of the subject.

